- Positive respiratory questionnaire endpoint (as defined above) on visit 4
- Positive respiratory questionnaire endpoint (as defined above) on visit 5
- Prevalence of IgG/IgM against SARS-CoV-2 among the total of screened participants
- Itemized analysis of each of the components of the respiratory questionnaire on each study visit
- The incidence of new cardiovascular events on each study visit
- Differences in repeated measurements of vascular parameters (arterial hardness, central arterial pressures, reflected waves, endothelial function and carotid medial sheath thickness) in visit 3 between the two sub-study groups (placebo or BCG)
- Differences in repeated measurements of vascular parameters (arterial hardness, central arterial pressures, reflected waves, endothelial function and thickness of medial carotid sheath) and cardiac ultrasound at visit 5 between the two sub-study groups (placebo or BCG)
- Changes in the release of cytokines from blood mononuclear cells at visit 3 between the two sub-study groups (placebo or BCG)

STUDY POWER CALCULATION

The study is powered for the primary endpoint. The results of the interim analysis of the ACTIVATE study reveal 20.4% incidence of total respiratory infections

after three months from vaccination in the placebo group and 12.2% in the BCG group. To demonstrate this difference with 90% power at the 5% level of significance, 437 people need to be vaccinated per group. To adjust for losses to follow-up, we target to enroll 450 people per group.

To estimate the power of the sub-study, it is anticipated that there will be a difference greater or equal to 2% in endothelial-dependent vasodilation between the two interventions in visit 5. A total sample of 68 patients (with equally 34 individuals in each study group placebo or BCG) will highlight a difference with a power of 80% at the 10% level of significance. In order to adjust for possible losses of 10%, it is estimated that 75 patients should be admitted to the sub-study.

STATISTICAL ANALYSIS

Comparisons between the two groups will be done by the Fisher exact test. Any value of p below 0.05 will be considered as significant.

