The differences in the repeated measurements of the vascular parameters (arterial hardness, central arterial pressures, reflected waves, endothelial function and thickness of the inner-middle carotid sheath) will be estimated using randomly mixed models with two types: random effects (random intercept and random slope) and variance-covariance matrix. Vascular parameters will be used as dependent variables, after checking the normal distribution of their residuals with histograms and Q-Q plots graphs. In case of irregular distribution, appropriate transformations will be used (based on the neural index or using inverse ranking normalization).

INTERIM ANALYSIS

The Sponsor will appoint an independent committee to analyze the study and report the results of the primary endpoint once the last enrolled subject will reach visit 3. The study investigators will be informed on the results of the interim analysis but they will remain blind to the allocated arm of vaccination which will allow the study to end after the last visit of the last subject.

ADVERSE EVENTS

Adverse events (AEs) and Serious Adverse Events (SAEs) will be collected from baseline until the last patient's evaluation. Investigators should monitor subjects for adverse events and are responsible for recording ALL adverse events and serious adverse events occurring to a patient during the trial. Infection will not be reported as an SAE since this is the study primary endpoint.

An adverse event is any undesirable medical occurrence in a subject administered a pharmaceutical product and which does not necessarily have a causal relationship with this treatment. The time relationship is defined from the moment the AE occurs during therapeutic treatment until 30 days or 5 half-lives after treatment discontinuation. The adverse event may be a sign, a symptom, or an abnormal laboratory finding.

Serious adverse events (SAEs) must be reported to within 24 hours. If an adverse event meets any of the following criteria, it is considered SAE:

- **Death**
- **Life-threatening situation** The subject was at risk of death at the time of the adverse event/experience. It does not refer to the hypothetical risk of death if the AE were more severe or were to progress.
- **Inpatient hospitalization** or prolongation of existing hospitalization.

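### The vascular sub-study is sized on one contrast at the 10% level, but its endpoint list gives at least ten vascular contrasts equal standing and the only stated significance threshold is 0.05

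*Protocol*

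**What the plan says.** **Sizing.** The Study Power Calculation section (repeated in the synopsis) anticipates that "there will be a difference greater or equal to 2% in endothelial-dependent vasodilation between the two interventions in visit 5". The size is given as "A total sample of 68 patients (with equally 34 individuals in each study group placebo or BCG"), and the claim made for that number is that it "will highlight a difference with a power of 80% at the 10% level of significance". Allowing for losses, "In order to adjust for possible losses of 10%, it is estimated that 75 patients should be admitted to the sub-study". No standard deviation is given, and the 10% is not said to be one- or two-sided.

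**Endpoints.** The Secondary endpoints section is an unranked list. One item is "Differences in repeated measurements of vascular parameters (arterial hardness, central arterial pressures, reflected waves, endothelial function and carotid medial sheath thickness) in visit 3". The next repeats the five parameters for the later visit and adds the heart: "endothelial function and thickness of medial carotid sheath) and cardiac ultrasound at visit 5 between the two sub-study groups (placebo or BCG"). Cytokine release at visit 3 is a further item. Endothelial-dependent vasodilation is not named there. It is covered only by endothelial function, which the Procedures of the Sub-study section describes as including both endothelium-dependent and nitrite-mediated dilation.

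**Analysis.** The Statistical Analysis section first names the Fisher exact test and then says: "Any value of p below 0.05 will be considered as significant". The next paragraph describes mixed models for the five vascular parameters: "Vascular parameters will be used as dependent variables". It names no lead parameter, deciding visit, model term or significance level.

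**The concern.** A power statement tells the reader which comparison a study is built to decide. Here that comparison is one variable at one visit. The endpoint list treats it as part of one item among many, and the analysis text handles all five parameters alike. Someone following the protocol as written could rest a claim of vascular effect on any of about ten contrasts, although the stated 80% power belongs to only one. The chance of a false nominal finding somewhere in the set is then well above 5%, and different parameters or visits may point in different directions with no rule for which one counts.

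The level is also unsettled. The sub-study is sized at 10%, while the only threshold for calling a result significant is 0.05. If 0.05 governs, the sized contrast does not have its stated power. If 10% governs, the chance of a false nominal finding across the list is higher still.

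What is at stake is the sub-study's claim about mechanism. The trial's primary endpoint is not affected.

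**Working it through.** **1. The stated sample size.** Inputs from the protocol: difference 2 percentage points, 34 per group, power 80%, level 10%. For two means, n per group = 2(z_α + z_β)²·SD²/Δ². The SD is not given, so 34 cannot be confirmed independently; the formula can only be solved for the SD.

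- 10% two-sided: z_α + z_β = 1.645 + 0.842 = 2.487, so SD = 2·√(34/2)/2.487 ≈ 3.3 points.
- 10% one-sided: 1.282 + 0.842 = 2.124, so SD ≈ 3.9 points.

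The loss allowance raises no issue: 68/0.9 = 75.6, that is 76 against the stated 75.

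**2. Power at the stated threshold.** If 34 per group gives 80% power at a two-sided 10% level, the expected test statistic is 2.487 whatever the SD. At two-sided 0.05:

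- Power = Φ(2.487 − 1.960) = Φ(0.527) ≈ 70%.
- Restoring 80% at 0.05 would take 34 × (2.802/2.487)² ≈ 43.2, so 44 per group, where 2.802 = 1.960 + 0.842.
- If the 10% is one-sided, power at two-sided 0.05 is lower: Φ(2.124 − 1.960) = Φ(0.164) ≈ 57%.

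**3. Number of contrasts.** Five parameters × two visits = 10, as the endpoint list reads. If the mixed model gives one treatment-by-time test per parameter, the count is 5. Cardiac ultrasound and cytokines are left out of both counts.

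**4. Chance of at least one nominally significant vascular difference with no vaccine effect.** For k independent two-sided tests at 0.05 this is 1 − 0.95^k:

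- k = 10: 1 − 0.95¹⁰ = 40.1%
- k = 5: 1 − 0.95⁵ = 22.6%

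For a common correlation ρ between test statistics and cut-off c = 1.960, it is 1 − ∫[Φ((c − √ρ·u)/√(1−ρ)) − Φ((−c − √ρ·u)/√(1−ρ))]^k φ(u) du. For the favourable direction only, the second Φ term is dropped. The documents give no correlation, so ρ is an assumption and is varied:

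| Assumed ρ | 10 contrasts, either direction | 10 contrasts, favourable only | 5 tests, either direction |
|---|---|---|---|
| 0 | 40.1% | 22.4% | 22.6% |
| 0.3 | 35.1% | 17.8% | 20.9% |
| 0.5 | 28.7% | 14.4% | 18.3% |
| 0.8 | 17.3% | 8.6% | 12.7% |

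With one pre-named contrast the rates would be 5% in either direction and 2.5% in the favourable direction.

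**5. If the sizing level were the threshold.** For ten contrasts each at two-sided 10%, the either-direction rate is 65.1% at ρ = 0 and 48.9% at ρ = 0.5.

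**The case against.** The strongest reply is that sizing a sub-study on one variable while listing others as secondary is ordinary practice. The order of secondary endpoints and any multiplicity rule are commonly left to the SAP, which is not shown. This stands to the extent that a missing adjustment is not the point here. What remains is that two parts of the protocol do not match: a power statement built on one contrast, and an endpoint list and analysis paragraph that do not identify it. The level in the power statement also differs from the only stated threshold.

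A second reply is that the 0.05 sentence directly follows the Fisher test sentence and may not govern the mixed models, whose paragraph speaks of estimating differences. That reading is possible. The only level attached to the sub-study would then be 10%, and the rates in step 5 would apply.

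A third reply is that the mixed model may give five tests, not ten. The text does not settle which term is tested, so both counts are shown.

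Some stronger readings are tempting but not supported:

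- *A vaccine with no effect would show a vascular benefit about 29% of the time.* That figure needs an assumed correlation of 0.5 and counts harm as well as benefit. At that correlation the favourable rate is about 14%.
- *The rates are lower bounds because some parameters contain several measurements.* Such measurements would probably be strongly correlated and add little, and a higher correlation lowers the rate.
- *The protocol says any one significant contrast establishes a vascular effect.* It does not. It only fails to say which contrast would.

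**Conclusion.** The point holds as a mismatch within the protocol. The sub-study is sized on endothelial-dependent vasodilation at visit 5, yet the endpoint list and the analysis paragraph give five vascular parameters at two visits the same standing and name no lead.

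With no vaccine effect, the chance of at least one nominally significant vascular difference at 0.05 is about 17% to 40% in either direction for ten contrasts. It is 13% to 23% if the model yields five tests, and about 9% to 22% in the favourable direction for ten contrasts. These ranges rest on an assumed common correlation between 0.8 and 0 and on 0.05 applying to the mixed-model comparisons.

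Separately, the 10% sizing level and the 0.05 threshold are not reconciled. If the 10% is two-sided, the sized contrast has about 70% power at p below 0.05, not 80%; this result does not depend on the unstated SD.

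The point deserves correction because it decides what the sub-study can conclude.

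**What to change.** In the Secondary endpoints section and the mixed-model paragraph:

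1. Name the between-group difference in endothelial-dependent vasodilation at visit 5, estimated from the mixed model, as the sub-study's single deciding contrast.
2. State one significance level for it, say that it is two-sided, and restate the power at that level: 80% at 10%, or about 70% at 5%, with the present 34 per group.
3. Label the visit 3 contrasts, the other vascular parameters, cardiac ultrasound and cytokine release as exploratory, reported as estimates with confidence intervals.

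The stated sizing refers to a difference at visit 5, not to change from visit 1. If the sponsor prefers change from visit 1, that is a new choice that may carry a different SD, and the power should be restated for it.

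The cost is protocol wording, with no additional patients, visits or measurements. The downside is that the other measures become supportive only and cannot carry the sub-study's conclusion.

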Power of the study	
The study is powered for the primary endpoint. The results of the interim analysis of the ACTIVATE study reveal 20.4% incidence of total respiratory infections after three months from vaccination in the placebo group and 12.2% in the BCG group. To demonstrate this difference with 90% power at the 5% level of significance, 437 people need to be vaccinated per group. To adjust for losses to follow-up, we target to enroll 450 people per group.
 
To estimate the power of the sub-study, it is anticipated that there will be a difference greater or equal to 2% in endothelial-dependent vasodilation between the two interventions in visit 5. It is estimated that a total sample of 68 patients (equally 34 individuals in each study group-placebo and BCG) will highlight the difference with 80% power at a statistical significance level of 10%. In order to adjust for possible loss of 10%, it is estimated that 75 patients should be admitted to the sub-study.

Interim analysis	
Taking into consideration the situation of COVID-19 pandemic, an interim analysis is decided by the Sponsor when all patients reach visit 3

Study duration	
12 months

BACKGROUND

Infection by the novel SARS-CoV-2 virus (also known as COVID-19) has tremendous social impact. Most of Western societies are at major or part lockdown whatever brings unpredictable financial and societal consequences. The urgent need for the reversal of this situation can only be met through the generation of an immune defence shield to protect the society from COVID-19. Many efforts for the development of a vaccine are under way without any specific outcome so far.

The stimulation of trained immune responses seems the only alternative to bridge the gap from the turn-on of the society until the entrance of a specific vaccine in the market. Trained immunity stands for the non-specific raise of defence shield for severe infections coming once tissue macrophages recognize a universal pathogen¹. The concept was successfully tested in healthy volunteers that were vaccinated with placebo or BCG (Bacillus Calmette Guérin) vaccine. These volunteers were injected 14 days later a tri-valent influenza A vaccine. Volunteers previously vaccinated by BCG developed significantly greater titres against hemagglutinin A of the influenza A virus whereas their circulating monocytes were more potent for the production of interferon-gamma².

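### The sub-study's 80% power is stated at a 10% significance level, but the only significance rule in the analysis section is p<0.05; on a two-sided reading, power at that rule is about 70%

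*Protocol*

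**What the plan says.** The Study Power Calculation section sizes the sub-study on "a difference greater or equal to 2% in endothelial-dependent vasodilation between the two interventions in visit 5". It asks for 68 participants, 34 per group, and says that this number "will highlight a difference with a power of 80% at the 10% level of significance". The synopsis (Power of the study) repeats the claim: the sample "will highlight the difference with 80% power at a statistical significance level of 10" percent. Neither place gives the sidedness of the 10% or the standard deviation behind the 2% difference.

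The Statistical Analysis section opens with the Fisher exact test for group comparisons and then sets its only threshold: "Any value of p below 0.05 will be considered as significant". The next paragraph covers the vascular parameters, whose differences "will be estimated using randomly mixed models with two types: random effects (random intercept and random slope) and variance-covariance matrix". It gives no significance level of its own.

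The vascular comparisons at visits 3 and 5 are listed among the secondary endpoints. The visit 5 vasodilation comparison is the only one of them with a power statement.

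**The concern.** A power figure is meaningful only at the level at which the test will be judged. Here the planning level is 10% and the declared level is 5%. With the same sample and effect, the stricter level gives lower power, so a reader who takes the 80% at face value overestimates the chance that the sub-study will detect the difference it was sized for.

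This affects how a non-significant vasodilation result is read, because a miss is more likely than the Protocol suggests. It also leaves the intended level for this comparison open to argument once results are known. The Protocol itself fixes both numbers, so this is not a detail left to a statistical analysis plan.

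**Working it through.** **Inputs from the Protocol.** Sub-study: n = 34 per group, power 80%, alpha 10% with sidedness not stated, difference 2 percentage points at visit 5, no SD. Analysis rule: p<0.05.

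**Can the plan's figure be reproduced?** Not from its own inputs, because the SD is missing. One can only solve for the SD that would make the claim exact. For two means and a two-sided 10% level:

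SD = 2 / [(z₀.₉₅ + z₀.₈₀) × √(2/34)] = 2 / [(1.645 + 0.842) × 0.2425] ≈ 3.32 percentage points.

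That value returns n = 34 and 80% power by construction. It is a back-calculation and not a figure from the Protocol.

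**Power at two-sided 5%.** This step does not need the SD. If the design has 80% power at two-sided 10%, the expected test statistic is z₀.₉₅ + z₀.₈₀ = 2.486. Then:

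Power = Φ(2.486 − 1.960) = Φ(0.526) = 0.701.

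The noncentral t distribution with 34 per group gives 0.697. If 34 was rounded up from as little as 33.01, the normal figure rises only to 0.713.

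**If the 10% was one-sided.** The expected statistic is z₀.₉₀ + z₀.₈₀ = 1.282 + 0.842 = 2.123. Power at two-sided 5% is Φ(2.123 − 1.960) = Φ(0.163) = 0.565 (noncentral t 0.558).

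| Planning level read as | Test judged at | Power, 34 per group (normal approximation) |
|---|---|---|
| two-sided 10% | two-sided 5% | 70% |
| two-sided 10% | one-sided 5% | 80% |
| one-sided 10% | two-sided 5% | 56% |
| one-sided 10% | one-sided 5% | 68% |

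**Which reading of p<0.05?** The Protocol states no one-sided test. The main trial's 437 per group (20.4% against 12.2%, 90% power, 5% level) lies close to the two-sided results, 425 without and 449 with continuity correction. It is far from the one-sided results, 346 and 370. That supports reading p<0.05 as two-sided.

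**How far the unknown SD matters.** The 70% assumes that the stated 80% is right. If it is not, power depends on the true SD. Assumed values, for illustration only:

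| Assumed SD (points) | Power at two-sided 10% | Power at two-sided 5% |
|---|---|---|
| 2.5 | 95% | 91% |
| 3.0 | 87% | 78% |
| 3.3 | 80% | 71% |
| 3.5 | 76% | 65% |
| 4.0 | 66% | 54% |

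**Scale of the gap.** To have 80% power at two-sided 5% for the same standardised difference, the design would need 34 × (2.802/2.486)² ≈ 43.2, so 44 per group, where 2.802 = 1.960 + 0.842.

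**The case against.** **The p<0.05 sentence may belong only to the Fisher test.** It follows directly on the Fisher sentence, and the mixed-model paragraph comes later. The 10% appears in both the synopsis and the body, so a deliberately looser level for a mechanistic sub-study is possible. But the sentence is worded for any p value. If it did not reach the mixed models, the analysis section would give the vascular comparisons no threshold at all. Either way the text needs one.

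**A mixed model on repeated measurements may have more power.** This is a fair limit on the 70%. Vascular ultrasound is scheduled at visits 1, 3 and 5. If the sizing ignored baseline, which is an assumption, the shortfall closes when the variance falls to (2.486/2.802)² = 0.79 of its unadjusted value. That takes a baseline correlation of about 0.46 with baseline adjustment (1 − ρ² = 0.79), or about 0.61 for change from baseline (2(1 − ρ) = 0.79). The Protocol gives no correlation and claims no such gain, so this does not rescue its wording. It does make the 70% conditional.

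**Stronger readings that the Protocol does not support.**
- A reader might infer that a p between 0.05 and 0.10 is significant under one section and not under the other. The power section sets a planning level and no decision rule. The one declared rule is 0.05.
- A reader might take about 70% as the established power. It depends on an unstated two-sided 10% and on an 80% that cannot be checked.
- A reader might treat an SD of 3.3 as the sponsor's input. It is only what the stated sample size implies.
- A reader might add that 75 to be admitted is an error, since 68/0.9 = 75.6. The figure matches 68 × 1.10 = 74.8 rounded up, and 75 × 0.9 = 67.5 is half a participant below 68. That is immaterial.

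**Conclusion.** The mismatch stands. The 80% belongs to a 10% level, and the only significance rule in the analysis section is 5%. Under the ordinary two-sided reading of both, power for a simple two-group comparison at visit 5 is about 70% for any SD, provided the stated 80% at 10% is correct. If the 10% was one-sided, it is about 56%. Only a two-sided 10% paired with a one-sided 5% test would keep 80%, and no one-sided test is stated.

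This is an inconsistency between sections and not a demonstrated error in a calculation. It concerns a secondary sub-study comparison. The primary endpoint and the main sample size are untouched. It should be corrected because the power claim is wrong as written for the declared rule and the correction is cheap.

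**What to change.** State one alpha and its sidedness for the visit 5 endothelium-dependent vasodilation comparison, in the same terms in the synopsis, the Study Power Calculation section and the mixed-model paragraph of Statistical Analysis. Changing only one of these would create a new inconsistency. Then choose one of the following:

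- **Keep p<0.05.** Restate the power of 34 per group at that level, about 70% under the two-sided reading. The sponsor should recompute it from its own SD and state that SD with its source. If it relies on a gain from repeated measurements, it should state the assumed correlation.
- **Keep 10%.** Declare in the analysis section, before unblinding, that this comparison is exploratory and tested at 10%, with the sidedness given. The SD should still be stated.

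The cost is wording and, under the first option, a less favourable stated power. No extra enrolment is needed. Re-sizing to 44 per group is possible but not required for a secondary mechanistic comparison, and the target of 75 can stay.

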The aim of the study is to demonstrate in a double-blind, placebo-controlled approach if vaccination of participants susceptible to COVID-19 with BCG vaccine may modulate their disease susceptibility for COVID-19. This will be validated using both clinical and immunological criteria. A sub-study will run in order to assess the mechanism of benefit from BCG vaccination on vascular endothelial function and on mononuclear blood cells.

STUDY DESIGN

Patient population

This is a prospective, multicenter, randomized, controlled trial in that will take place in departments in Greece (APPENDIX II). The study will be submitted for approval by the National Ethics Committee of Greece and by the National Organization for Medicines of Greece. Patients will be enrolled after written informed consent provided by themselves or provided by legal representative in case of patients unable to consent.

Inclusion criteria

Enrolled patients should meet all following inclusion criteria:

1. Written informed consent
2. Male or female

3. Age more than or equal to 50 years based on the precise date of birth. Female participants are allowed on the premise that they are post-menopausal.
4. History of at least one of the following: a) coronary heart disease; b) chronic obstructive pulmonary disease; c) Charlson's comorbidity index (CCI) more than 3 (APPENDIX III)
5. Skin tuberculin test diameter less than 10mm
6. Negative serum testing for immunoglobulin G and M against SARS-CoV-2

Exclusion criteria

Patients meeting ANY of the following should NOT be enrolled.

- Deny to written informed consent
- Age less than 50 years
- Known infection by the Human Immunodeficiency Virus-1 (HIV-1)
- Severely immunocompromised patients. This exclusion category comprises:
 - History of congenital immunodeficiency
 - History of solid organ transplantation
 - History of bone marrow transplantation
 - Intake of chemotherapy the last two months
 - Intake of radiotherapy the last two months
 - Active hemalogical or solid tumor malignancy
 - History of any anti-cytokine therapies
 - History of oral or intravenous steroids defined as daily doses of 10mg prednisone or equivalent for longer than the last 3 months

Study interventions

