Participants will be randomized at 1:1 ratio by a separate list per study site into two treatment groups. The list of randomization will be generated by a biostatistician and the randomization will be in a sealed envelope. The envelope will be delivered to the attending physicians after randomization. The two groups of treatment will be as follows:

- Placebo group: these participants will receive one intradermal injection of 0.1ml of sodium chloride 0.9%

- BCG group: these participants will receive one intradermal injection of 0.1ml of BCG (Bacillus Calmette Guérin Moscow strain 361- I, Serum Institute for India)

Patient screening and enrolment (APPENDIX IV)

In order for screening to proceed, the study will be advertised in the study site of the Hellenic Institute for the Study of Sepsis (www.sepsis.gr) and in the sites of other medical societies. The text to be used for the study advertisement is provided in APPENDIX V. People who will collaborate for the patient information will be GCP certified by the Sponsor.

Screening may start only after written informed consent is provided. Once written informed consent is provided, screening follows the following order:

- The patient is screened against the exclusion criteria. If the patient does not meet any exclusion criteria, screening proceeds to the next step.
- The patient is screened for inclusion criteria 1 to 4. If he does not meet all of them, it is a screening failure and screening stops. If he meets all of them, screening proceeds to the next step.
- The PPD Skin Test (inclusion criterion 5) is performed with an intradermal tuberculin injection into an forearm according to the manufacturer's instructions. The patient is asked to return in 48 hours to measure the skin hardness. If the diameter of the skin hardness is greater or equal to 10mm, it is considered as failure and screening process ends. If the diameter of the skin hardness is less than 10mm, screening process proceeds to the next step. This step can be omitted for patients who have undergone tuberculosis skin testing or a positive indirect detection test for *Mycobacterium tuberculosis* by determination of interferon- γ (IFN γ) after excitation of the last CD4- /CD8- cells for special peptides (IGRA) within the past five (5) years. In this case, any skin reaction with a fraction of less than 10 millimeters or a negative IGRA test allows the patient to enter the study.

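### Randomisation is by site but the fixed test is an unstratified Fisher exact test: a site-stratified Cochran-Mantel-Haenszel test would gain about 1.3 to 3 points of power at no cost (efficiency, not validity)

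*Protocol*

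**What the plan says.** - Protocol, Study Design, Patient population: "This is a prospective, multicenter, randomized, controlled trial".
- Protocol, Study interventions: "Participants will be randomized at 1:1 ratio by a separate list per study site into two treatment groups". Neither the use of blocks nor a block size is stated.
- Protocol, Statistical Analysis: "Comparisons between the two groups will be done by the Fisher exact test", followed by "Any value of p below 0.05 will be considered as significant". No stratification factor or covariate is named for this comparison, and the section does not defer to another document. Whether the threshold is one- or two-sided is not stated.
- Protocol, Study Power Calculation: the planning rates are "20.4% incidence of total respiratory infections" "after three months from vaccination in the placebo group and 12.2% in the BCG group". The size follows: "To demonstrate this difference with 90% power at the 5% level of significance, 437 people need to be vaccinated per group", then "To adjust for losses to follow-up, we target to enroll 450 people per group". The test behind 437 is not named.

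**The concern.** Two separate features of the fixed test cost power.

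1. **Fisher is conservative.** Because the counts are discrete, its true rejection rate under the null lies below the nominal 5%. With more than 400 people per group there is no small-sample reason to accept this.
2. **The test ignores site.** Where allocation is balanced within sites and event risk differs between sites, as SARS-CoV-2 exposure may, a pooled test uses a variance that includes between-site differences which cannot bias the comparison. The test then becomes more conservative still. A test stratified by the factor used in randomisation removes that excess.

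At stake is the chance of detecting a real effect from the same participants. A false-positive result is not made more likely.

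**Working it through.** **Inputs.** From Study Power Calculation: p1 = 0.204, p2 = 0.122, 5% level, 90% power, 437 per group needed, 450 enrolled (allowance 13/450 = 2.9%). From Statistical Analysis: Fisher, p < 0.05, taken as two-sided.

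**Step 1: the protocol's own figure.** With mean rate 0.163,

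n = [1.96·√(2·0.163·0.837) + 1.2816·√(0.204·0.796 + 0.122·0.878)]² / 0.082²
= [1.96·√0.27286 + 1.2816·√0.26950]² / 0.006724
= (1.0238 + 0.6653)² / 0.006724 ≈ 424.3, so 425 per group.

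The continuity correction gives 449. The stated 437 lies 12 from each (2.7%), so it is reproduced to within rounding of method. One-sided formulas give 346 or 370 and do not fit, which supports the two-sided reading.

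**Step 2: Fisher against chi-square, exact.** Every pair of counts (x, y) from two binomials was enumerated, and the probabilities of the pairs that each test rejects were summed. Chi-square is uncorrected.

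| Per group | True rates | Fisher | Chi-square |
|---|---|---|---|
| 437 | 16.3% in both (size) | 4.1% | 5.0% |
| 437 | 20.4% vs 12.2% | 89.6% | 91.1% |
| 450 | 20.4% vs 12.2% | 90.4% | 91.9% |
| 405 (10% loss, assumed) | 20.4% vs 12.2% | 87.1% | 88.9% |

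The cost of Fisher at 437 is 91.1 − 89.6 = 1.5 points. The smallest group size giving 90% power is about 445 for Fisher and about 420 for chi-square.

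**Step 3: lower event rates (assumed), 437 per group, risk ratio held at 0.6.**

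| True rates | Fisher | Chi-square | Loss (points) |
|---|---|---|---|
| 15% vs 9% | 75.4% | 78.6% | 3.2 |
| 10% vs 6% | 54.4% | 59.4% | 5.1 (before rounding) |
| 5% vs 3% | 27.0% | 32.2% | 5.2 |

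At a common rate of 5%, Fisher's size is 3.5% and chi-square's 4.9%.

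**Step 4: adding site strata, simulated.** 20,000 runs per setting, 437 per group, balanced within site, with mean rates of 20.4% and 12.2% (20.4% in both for size). The number of sites (5, 10, 20) and the between-site SD of the log odds are assumptions. Ranges are over the number of sites.

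| Between-site SD | Fisher size | CMH size | Fisher power | CMH power | Gain (points) |
|---|---|---|---|---|---|
| 0 | 4.2–4.3% | 4.9–5.2% | 89.3–90.1% | 90.8–91.3% | 1.3–1.5 |
| 0.5 | 3.6–3.7% | 4.7–5.0% | 89.7–89.8% | 91.6% | 1.8–1.9 |
| 1.0 | 2.8–3.2% | 4.8–5.1% | 90.8–91.3% | 93.6–94.0% | 2.7–3.0 |

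The Monte Carlo standard error of a power near 90% is √(0.9·0.1/20,000) = 0.2 points. At SD 0.5 most of the gain comes from leaving Fisher (1.5 points exactly); the site strata add only about 0.5 point.

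**Step 5: without within-site balance.** In a separate simulation (10 sites, about 435 per arm, 16.3% in both arms, unblocked lists), Fisher's size stayed at 4.3–4.5% at every SD from 0 to 1.0.

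**The case against.** The strongest reply is that Fisher is valid, pre-specified and light on assumptions, and that the sample size already carries most of its cost: 437 is 12 above the uncorrected figure of 425, and Fisher needs about 445. This stands. The shortfall at 437 is 0.4 points (about 8 people per group), and none remains at 450.

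It is also fair to say that pooling rules, covariate lists and the effect estimate usually belong in a SAP, which was not available. Their absence is therefore not criticised. The test itself is different: the protocol names it without qualification, so a SAP with a stratified primary test would depart from the protocol.

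Three stronger readings are tempting, and the document does not support them.

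- **A reader might infer that the real type I error is well under 5%.** Exactly computed at the planning rates it is about 4%. It falls to around 3% only with within-site balance and strong site differences, neither of which the protocol states.
- **A reader might infer that the promised 90% power is lost.** The figures for 437 and 450 show that it is essentially met at the planned rates and losses.
- **A reader might infer a sizeable further gain from stratifying by COPD**, citing the odds ratio of 3.14 in Appendix I, Table 4. That ratio concerns any infection over 12 months in recently hospitalised people aged 65 or over. This trial has a 90-day COVID-19 composite in people aged 50 or over, with COPD itself a route to entry. The prevalence of COPD here is also not given, so no size can be put on the gain.

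**Conclusion.** The point holds as a free improvement in efficiency. The analysis does not use the factor by which participants are randomised, and Fisher alone costs 1.5 points of power at the planned rates; this part is exact and rests only on the protocol's figures with a two-sided test. Replacing it with a site-stratified CMH test gains about 1.3 to 2 points with no or moderate site variation and up to about 3 with strong variation, given the assumed number of sites, spread and within-site balance.

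The loss matters more if events are scarcer than planned (about 5 points at 10% versus 6%, assumed). It also matters more if losses exceed the 2.9% allowance, since Fisher's power falls to 87.1% at 405 per group. Type I error is controlled throughout, and a significant Fisher result would be sound.

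**What to change.** In Statistical Analysis, name the Cochran-Mantel-Haenszel test stratified by site, two-sided at 5%, as the primary test. Report a common (Mantel-Haenszel) risk difference or risk ratio with its 95% CI. Pool small sites by a rule written down before unblinding. Keep the Fisher exact test as a sensitivity analysis.

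The change must be in place before the independent committee analyses the primary endpoint at visit 3, because a switch to a more powerful test after that would not be credible. The cost is a change of wording: no new data, participants or procedures are needed, and the sample size can stay as it is.
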